### **REVISION HISTORY**

Revision #	Version Date	Summary of Changes
AM1	v 2.0: 01JUL2020	Recruitment materials Oral consent and phone screen questionnaire for prescreening Language in protocol to reflect the recruitment process and consenting process
AM2	V3.0 10SEP2021	Increased COVID sample population from 30 to 75 and decreased minimum time between collections to 15 min.

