## Detection of SARS-CoV-2 RNA and Biomarkers in Coughed Droplets from Patients with COVID-19 and Controls

### 1. Study Summary

Study Title	Detection of SARS-CoV-2 RNA and Biomarkers in Coughed Droplets from Patients with COVID-19 and Controls
Study Design	Single Center comparative trial with controls
Primary Objective	Determine the sensitivity and specificity of detecting SARS-CoV-2 RNA in cough-generated droplets captured with the PneumoCheck™
Secondary Objective(s)	Determine the value of detecting inflammatory cytokines and chemokines and other biomarkers in cough-generated droplets with PneumoniaCheck in evaluating disease in COVID-19 patients.
Research Intervention(s)/Interactions	Determine the value of PneumoniaCheck specimens for diagnosing SARS-CoV-2 infection and assessing disease state and understanding pathogenesis of disease.
Study Population	We will enroll up to 30 SARS-CoV-2 PCR positive patients and up to 30 patients with a non-COVID-19 acute respiratory illness being treated either as inpatients or outpatients to participate in the study. We will also enroll up to 30 healthy controls.
Sample Size	Up to 135 across all cohorts
Study Duration for individual participants	Those who consent to participate will have a cough specimen collected over the following 24 hours and asked to do 4 additional sets of 10 coughs into the same device
Study Specific Abbreviations/ Definitions	NA
Funding Source (if any)	Internal funding in addition to Georgia Tech grant

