## Detection of SARS-CoV-2 RNA and Biomarkers in Coughed Droplets from Patients with COVID-19 and Controls

PneuCk 7	neg	30.08	neg	517.6
PneuCk 8	neg	neg	neg	3.92
PneuCk 9	neg	neg	neg	0.04
Sputm 1	neg	36.89	35	1293
Sputm 2	neg	27.62	neg	6494

**Table 1.** Pathogen detection and specimen quality determination. PneumoniaCheck specimens were collected in 9 CF patients and 2 non-CF control patients by 5 different collections of 10 coughs with each collection separated by > 1 hour. The device was stored at -80°C until processing. The specimen was

eluted from the filter and tested for *Staphylococcus aureus* (Staph A), *Pseudomonas aeruginosa* (Pseud A), and *Streptococcus pneumoniae* (Strep Pn) DNA by PCR, surfactant A (Surf A) by EIA, and amylase (Amyl) by an enzymatic assay. Neg = negative by PCR. Values are PCR CT values except for Amyl/SurfA which is the ratio of Amylase concentration over surfactant A concentration. Note the much higher Amyl/SurfA ratio for the sputum compare to PneumoniaCheck specimens indicating much lower or negligible levels of upper respiratory tract secretions in the specimen.

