### **10. Inclusion and Exclusion Criteria**

We will enroll up to 75 adult SARS-CoV-2 PCR positive patients and up to 30 adult patients with a non-COVID-19 acute respiratory illness being treated either as inpatients or outpatients to participate in the study. We will also enroll up to 30 adult healthy controls. We will collect coughed specimens during 5 sessions of 10 or more coughs separated by at least 15 minutes. Patients who consent to participate in the study will be instructed on method of collection and asked to collect 5 sets of 10 cough specimens over the next 24 hours with the same PneumoniaCheck device. After specimen collection is completed, the device is transferred to the laboratory and stored for processing. For processing, the filter (see **Figure 1**) with the captured coughed droplets is removed from the device, captured droplets eluted from the filter, and the eluate and filter are stored at -80°C for later testing, PCR for SARS-CoV-2 RNA, multiplex Luminex and Simoa Quanterix system assays for biomarkers of inflammation, enzyme immunoassay (EIA) for surfactant A, and an enzymatic assay for amylase. The PCR results, positivity and CT values, in

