### **17. Data Management and Confidentiality**

**Data Analysis.** Data will be analyzed based on specimen identification number and group (e.g., COVID-19 patient, non-COVID-19 acute respiratory illness patient, control).

The quality of the specimen captured on the filter, i.e. from the lung or upper respiratory or both will be indicated by surfactant A (lung) and amylase (upper respiratory).

The PCR results will be analyzed as positive or negative and by CT value. The PCR results in COVID-19 patients will indicate the sensitivity of this specimen for detecting SARS-CoV-2 RNA and PCR results in non-COVID-19 patients and controls the specificity. The ratio of surfactant A to amylase indicate lung and upper respiratory contributions to the specimen for all groups. The multiplex Luminex data or Simoa Quanterix system will give biomarkers of inflammation for each group. We will also test some specimens with mass spectrometry to identify novel biomarkers associated with COVID-19 lung disease. Specimens will be saved for additional future research testing.

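### AM2 raised only the COVID-19 cap and shortened the minimum collection interval in one step, so collection rule and period could be confounded with disease group in the Aim 2 biomarker contrasts

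*Protocol*

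**What the plan says.** The Revision History dates AM2 as "V3.0 10SEP2021" and describes two changes made together: "Increased COVID sample population from 30 to 75 and decreased minimum time between collections to 15 min". It names no increase in the other cohorts.

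Section 10 carries the new COVID-19 cap: "We will enroll up to 75 adult SARS-CoV-2 PCR positive patients and up to 30 adult patients with a non-COVID-19 acute respiratory illness". It continues: "We will also enroll up to 30 adult healthy controls". The 15-minute minimum follows these sentences and is worded for all cohorts. It applies to five sets of coughs into one device within 24 hours.

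On analysis, Section 17 states: "Data will be analyzed based on specimen identification number and group". Sensitivity comes from the COVID-19 patients and specificity from the other two groups. Section 10 takes biomarker differences between groups as associated with COVID-19. Neither section mentions protocol version, enrolment period or actual spacing of the sets.

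The only other interval in the document is in Table 1 (Section 4), for preliminary work in cystic fibrosis patients and non-CF controls: "with each collection separated by > 1 hour". The minimum that applied in this study before AM2 is not stated.

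**The concern.** An amendment that changes how specimens are taken does little harm to a group comparison if every group straddles it in similar proportion. Here the same amendment also enlarged one group and not the others, so the proportions can easily differ.

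Three things may then move together with disease group:

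- **Spacing of the sets.** All sets go into one device kept in a cooler between sets (Sections 5 and 6). Four gaps of 15 minutes allow completion in about 1 hour. Four gaps of more than 1 hour, as in the preliminary work, take more than 4 hours.
- **Calendar period**, before or after September 2021.
- **Time in the freezer.** Devices and eluates are held at -80°C and tested later.

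If any of these affects measured cytokines, chemokines, surfactant A or amylase, a by-group contrast could credit the effect to COVID-19. For Aim 1, a single sensitivity figure could average two collection rules without showing it.

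**Working it through.** **1. The plan's own total.** Section 1 gives "Up to 135 across all cohorts". The caps in Section 10 sum to 75 + 30 + 30 = 135, so the figure reproduces. With the earlier COVID-19 cap the sum is 30 + 30 + 30 = 90. The difference of 45 is exactly the COVID-19 increase, which fits an enlargement of that cohort alone.

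**2. COVID-19 share collected after AM2.** At most 30 could be enrolled under the earlier cap, so with N enrolled in all the minimum post-AM2 share is (N - 30)/N. This counts one device per participant; Section 9 allows some participants to give later samples.

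| COVID-19 enrolled (N) | Minimum post-AM2 | Share |
|---|---|---|
| 45 | 15 | 33% |
| 60 | 30 | 50% |
| 61 | 31 | 51% |
| 75 | 45 | 60% |

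A majority is therefore guaranteed only if more than 60 enrol. At N = 75 the share is 60%, 73%, 87% or 100% if 30, 20, 10 or 0 were enrolled before AM2.

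**3. Comparison share.** Nothing fixes how many of the 30 + 30 = 60 comparison participants come after AM2. At N = 75, the gap (COVID-19 share minus comparison share) is:

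| Comparison participants post-AM2 | Share | Gap if COVID-19 share is 60% | Gap if it is 100% |
|---|---|---|---|
| 0 of 60 | 0% | +60 points | +100 points |
| 30 of 60 | 50% | +10 points | +50 points |
| 36 of 60 | 60% | 0 | +40 points |
| 60 of 60 | 100% | -40 points | 0 |

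**4. What a gap would do (illustration only).** The documents give no effect of interval, period or storage on any biomarker, so the effects below are assumptions. Bias = gap × assumed effect in SD. With 75 versus 60 participants the standard error is √(1/75 + 1/60) = 0.173 SD. The false-positive rate is for a two-sided 0.05 test with no disease effect, by normal approximation.

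| Assumed effect | Gap +60: bias, false-positive rate | Gap -40: bias, false-positive rate |
|---|---|---|
| 0 SD | 0, 5% | 0, 5% |
| 0.2 SD | 0.12 SD, 11% | -0.08 SD, 7.5% |
| 0.5 SD | 0.30 SD, 41% | -0.20 SD, 21% |
| 0.8 SD | 0.48 SD, 79% | -0.32 SD, 46% |

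With a zero gap the bias is zero whatever the effect.

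**5. Aim 1.** If detection were 80% in 30 patients before AM2 and 70% in 45 after it (assumed), pooled sensitivity would be (30 × 0.80 + 45 × 0.70)/75 = 74%, which describes neither rule. No comparison participant enters this figure, so it is pooling and not confounding with disease.

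**The case against.** The strongest reply is that this belongs to a statistical analysis plan, which may exist and is not shown. Section 17 is an outline. It names group as a basis for analysis without excluding others, and the specimen number links to clinical data, so analysis by date or version remains possible. That stands for the modelling. It does not answer two matters of conduct. The data items listed in Section 6 include no set times, and no later analysis can create overlap if a comparison cohort was enrolled wholly on one side of AM2.

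Three stronger readings are tempting, and the documents do not support them:

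- **That most COVID-19 devices certainly fall under the new rule.** The 75 is an upper limit; with 45 enrolled the guaranteed share is only 33%.
- **That the comparison groups were collected under the old rule, so that rule and disease are confounded in fact.** Section 10 applies the 15-minute minimum to every cohort, and accrual by group before AM2 is not given. The imbalance could be large, nil or reversed.
- **That the interval fell from more than 1 hour to 15 minutes.** The longer interval belongs to the preliminary work. AM2 lowered a minimum, and participants may still space sets widely within 24 hours. Nothing in the document says that spacing affects yield.

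**Conclusion.** The point holds as a risk and is minor. One amendment enlarged only the COVID-19 cohort and relaxed the collection rule for everyone. At full enrolment at least 60% of COVID-19 participants are collected after it, against an unfixed 0% to 100% of comparison participants. Collection rule, calendar period and storage time could therefore be confounded with disease group in the Aim 2 contrasts. Aim 1 sensitivity only pools two rules.

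This rests on the cap of 30 having been respected before AM2, on one device per participant, and on the COVID-19 cohort filling. The size and direction of any bias are unknown, and the study's earlier minimum is not given. No view is taken on which interval is preferable.

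**What to change.** In the procedures (Section 6) and Section 17:

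1. Record the protocol version in force for every device and, from now on, the actual times of the five sets.
2. Report the numbers collected before and after AM2 in each of the three groups.
3. Report sensitivity overall and by version.
4. Stratify between-group biomarker comparisons by version where the groups overlap, and add a sensitivity analysis restricted to participants collected under the same version.
5. Enrol any comparison places still open concurrently with COVID-19 participants under v3.0.

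The cost is a short collection log and slightly wider intervals for stratified contrasts. Set times may not be recoverable for devices already collected; for those, version is the only handle. If the counts in item 2 prove balanced, the concern over the group contrast largely falls away.

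Separately, Section 1 still reads "We will enroll up to 30 SARS-CoV-2 PCR positive patients and up to 30 patients with a non-COVID-19 acute respiratory illness" and Section 12 still gives a total of 90. Both should be reconciled with the 75 in Section 10 and the total of 135.

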## Detection of SARS-CoV-2 RNA and Biomarkers in Coughed Droplets from Patients with COVID-19 and Controls

### 1. Study Summary

Study Title	Detection of SARS-CoV-2 RNA and Biomarkers in Coughed Droplets from Patients with COVID-19 and Controls
Study Design	Single Center comparative trial with controls
Primary Objective	Determine the sensitivity and specificity of detecting SARS-CoV-2 RNA in cough-generated droplets captured with the PneumoCheck™
Secondary Objective(s)	Determine the value of detecting inflammatory cytokines and chemokines and other biomarkers in cough-generated droplets with PneumoniaCheck in evaluating disease in COVID-19 patients.
Research Intervention(s)/Interactions	Determine the value of PneumoniaCheck specimens for diagnosing SARS-CoV-2 infection and assessing disease state and understanding pathogenesis of disease.
Study Population	We will enroll up to 30 SARS-CoV-2 PCR positive patients and up to 30 patients with a non-COVID-19 acute respiratory illness being treated either as inpatients or outpatients to participate in the study. We will also enroll up to 30 healthy controls.
Sample Size	Up to 135 across all cohorts
Study Duration for individual participants	Those who consent to participate will have a cough specimen collected over the following 24 hours and asked to do 4 additional sets of 10 coughs into the same device
Study Specific Abbreviations/ Definitions	NA
Funding Source (if any)	Internal funding in addition to Georgia Tech grant

### 2. Objectives

Goal: Determine the value of PneumoniaCheck specimens for diagnosing SARS-CoV-2 infection and assessing disease state and understanding pathogenesis of disease.

Aim 1: Determine the sensitivity and specificity of detecting SARS-CoV-2 RNA in cough-generated droplets captured with the PneumoCheck™

Aim 2: Determine the value of detecting inflammatory cytokines and chemokines and other biomarkers in cough-generated droplets with PneumoniaCheck in evaluating disease in COVID-19 patients.

### 3. Background

A novel coronavirus (SARS-CoV-2) was detected in association with cases of severe respiratory illness and pneumonia (COVID-19) in Wuhan City, Hubei Province, China in December 2019(1). The virus

[figure not shown]

## Detection of SARS-CoV-2 RNA and Biomarkers in Coughed Droplets from Patients with COVID-19 and Controls

subsequently spread widely throughout China and globally. As of June 2 2020, over 6,000,000 cases and 375,000 deaths have been reported globally and over 1,700,000 cases and 100,000 deaths in the United States(2). Addressing this unprecedented global pandemic is requiring all available tools to diagnose infection, manage ill patients, understand disease pathogenesis and virus transmission to guide efforts to decrease transmission and rapidly develop anti-viral drugs and vaccines. We propose to use the PneumoniaCheck™, a device developed collaboratively by investigators at Georgia Institute of Technology (GA Tech) and the Centers for Disease Control and Prevention (CDC), to help address these issues. This device, non-invasively, captures coughed droplets onto a filter with minimal contamination from upper airway secretions(3, 4). In preliminary studies in cystic fibrosis, mycobacterium tuberculosis (TB) patients and control patients, we detected bacterial DNA by PCR, inflammatory cytokines and chemokines by multiplex Luminescent assays, surfactant by enzyme immunoassay (EIA), and amylase by enzymatic assay. These data show that this device can provide high quality specimens from the lung with minimal risk to the patient and healthcare provider and much lower risk than invasive procedures such as bronchioloalveolar lavage. In addition, with this device, we can acquire specimens from patients who do not have a productive cough (dry cough), a commonly reported symptom for COVID-19, and specimens with minimal upper respiratory contamination unlike a sputum specimen. Thus, this device can provide lung secretion specimens to improve detection of SARS-CoV-2 RNA (lung specimens are better for detecting virus than upper respiratory tract specimens) and detect inflammatory and other biomarkers to explore pathogenesis of disease, identify inflammatory processes that might be amenable to intervention, and identify biomarkers of disease severity for patient management and evaluation of vaccines and anti-viral drugs. We propose to determine how PneumoniaCheck™ can help diagnose, manage, and understand pathogenesis of disease and transmission risk of COVID-19.

The PneumoniaCheck uses fluid mechanics to preferentially eliminate upper respiratory contaminants while capturing cough-generated droplets from the lung onto a filter. The device, illustrated in Figure 1, is designed to prevent upper respiratory tract fluids from entering the device, to direct residual upper airway (dead space) that may contain upper respiratory tract contaminants to a balloon, and to direct coughed air from the lung through a filter. Once the balloon is filled with dead space air, air from the lung is diverted through the filter and the droplets captured onto the filter. DNA or RNA from bacteria, viruses, etc., or proteins and other molecules present in these droplets can be detected by real time PCR for DNA or RNA or by enzyme immunoassays (EIAs) for cytokines, chemokines, or other molecules. The ability to detect SARS-CoV-2 RNA and biomarkers indicative of inflammation and active disease should help physicians manage COVID-19 patients and researchers understand the disease process and possibly transmission risk. This study will develop data on detection of SARS-CoV-2 RNA and lung biomarkers with this device in COVID-19 patients.

**Figure 1.** PneumoniaCheck.

[figure not shown]

## Detection of SARS-CoV-2 RNA and Biomarkers in Coughed Droplets from Patients with COVID-19 and Controls

### 4. Study Endpoints

Aim 1. Determine the sensitivity and specificity of detecting SARS-CoV-2 RNA in cough-generated droplets captured with the PneumoCheck™. We have captured real time PCR detectable bacterial DNA from the lung with PneumoCheck™ in the lung of adults with cystic fibrosis at a rate similar to that reported for detecting bacteria in bronchoalveolar lavage fluid (BALF) specimens by culture(3). Since high levels of SARS-CoV-2 RNA can be detected in sputum specimens, the coughed specimens are a promising specimen to detect SARS-CoV-2 RNA for diagnosis, monitoring course of disease, and possibly indicating risk of transmitting virus to others.

Aim 2. Determine the value of detecting inflammatory cytokines and chemokines and other biomarkers in cough-generated droplets with PneumoniaCheck in evaluating disease in COVID-19 patients. We previously demonstrated that with PneumoniaCheck that we can detect inflammatory biomarkers in patients with acute respiratory illness as illustrated in **Figure 2**. Using the amylase to indicate upper respiratory origin and surfactant A to indicate lower respiratory tract origin, we demonstrate that PneumoniaCheck specimens come primarily from the lower respiratory tract (**Table**). We now propose to detect biomarkers of inflammation in coughed specimens from patient with COVID-19. We hypothesize that biomarkers of inflammation from the lung will indicate disease activity, inform pathogenesis of COVID-19 disease.

## Detection of SARS-CoV-2 RNA and Biomarkers in Coughed Droplets from Patients with COVID-19 and Controls

PneuCk 7	neg	30.08	neg	517.6
PneuCk 8	neg	neg	neg	3.92
PneuCk 9	neg	neg	neg	0.04
Sputm 1	neg	36.89	35	1293
Sputm 2	neg	27.62	neg	6494

**Table 1.** Pathogen detection and specimen quality determination. PneumoniaCheck specimens were collected in 9 CF patients and 2 non-CF control patients by 5 different collections of 10 coughs with each collection separated by > 1 hour. The device was stored at -80°C until processing. The specimen was

eluted from the filter and tested for *Staphylococcus aureus* (Staph A), *Pseudomonas aeruginosa* (Pseud A), and *Streptococcus pneumoniae* (Strep Pn) DNA by PCR, surfactant A (Surf A) by EIA, and amylase (Amyl) by an enzymatic assay. Neg = negative by PCR. Values are PCR CT values except for Amyl/SurfA which is the ratio of Amylase concentration over surfactant A concentration. Note the much higher Amyl/SurfA ratio for the sputum compare to PneumoniaCheck specimens indicating much lower or negligible levels of upper respiratory tract secretions in the specimen.

### 5. Study Intervention/Investigational Agent

**Description:** The PneumoniaCheck is a device uses fluid mechanics to preferentially eliminate upper respiratory contaminants while capturing cough-generated droplets from the lung onto a filter. The device, illustrated in Figure 1 above.

**Device Handling:** The patient will be given the PneumoniaCheck device with a sterile ziplock bag and cooler with cold packs to keep the device, shown a video, given verbal guidance for collecting the first set of coughed specimens, and asked to do 4 additional sets of 10 coughs into the same device. The device will be stored in the ziplock bag in the cooler between collections.

### 6. Procedures Involved:

Patients seen at Emory COVID-19 testing centers will be asked to participate in the study. Those who consent to participate will have a cough specimen collected over the following 24 hours and their medical record will be reviewed for age, sex, race/ethnicity, underlying medical conditions, their SARS-CoV-2 PCR test results, and other diagnostic test results if being seen for a COVID exposure or illness or other acute respiratory illness. The patient will be given the PneumoniaCheck device with a sterile ziplock bag and cooler with cold packs to keep the device, shown a video, given verbal guidance for collecting the first set of coughed specimens, and asked to do 4 additional sets of 10 coughs into the same device. The device will be stored in the ziplock bag in a cooler between collections. After the specimen is collected, the specimen will be collected by study personnel and transported using standard operating procedures for specimen transportation to the laboratory. In the laboratory, in a BSL2 biosafety cabinet with BSL2+ conditions, the PneumoniaCheck will be double bagged for storage at -80°C. Later the specimen is processed and tested for SARS-CoV-2 RNA by real time PCR and biomarkers by a multiplex Luminex assay and mass spectrometry. Each specimen will be given an identification number, without personal identifying information, which will be used to link laboratory results to clinical and epidemiologic data.

